## MATERIALS AND METHODS

This was a prospective, randomized, observational study performed in 2 months in the Delivery Room of the Department of Obstetrics and Gynecology by the Newborn Department where approximately 3,500 infants are delivered annually. Stabilization followed the NRP guidelines and is implemented by a neonatology fellow and three pediatric assistants with NRP certificates. Single, term, appropriate for gestational age (AGA) babies who did not need resuscitation and babies in whom skin-to-skin contact cannot be applied were included in the study. Vaginal births were not included, only babies born with cesarean sectio (CS) and couldnot not exposed to early skin-to-skin contact were included.

---

Spinal anesthesia was used for the mothers for CS, mother was not given oxygen therapy until the baby came out. Parents were informed of the study prior to birth and written consent was obtained from those who were willing to participate. The babies were randomized by opening of envelopes containing positional codes and were placed supine, on the right or left side, or prone (15/group).

### **2. Medical records and vital parameters:**

All evaluations commenced 30 s after delivery and terminated at 10 min. For each infant, the 1st and 5th min Apgar scores were calculated by the same person, and the heart rate (HR), pulse oximetry, and perfusion index (PI) were recorded at 2nd, 5th, and 10th min using a Masimo Radical-7 pulse co-oximetry with an adhesive sensor. The probe was placed preductally (on the right wrist) and then connected to the oximetry. The fraction of inspired oxygen (FiO2) was only 0.21 ("room-air") during all the stabilization period. In line with the NRP 2015 guideline,

aspiration was not routinely performed in the delivery room; the number of times that touch stimulation was required and the tactile stimulus time were recorded. Although electrocardiography (ECG) recommended in the latest guidelines and reads heart rate much faster, pulse oximetry had to be used in our study because the relationship between position and saturation and cerebral oximetry was evaluated.

### **3.Cerebral oxygenation:**

Near-infrared spectroscopy (NIRS), which measures tissue oxygenation noninvasively, was used to evaluate cerebral oxygenation; the mean values at 5th and 10th min were recorded using a Covidien INVOS 5100C instrument. The cerebral regional cerebral oxygen saturation (rScO2) is the ratio of cerebral oxygenated hemoglobin (CHbO2) to the total oxygen bound to cerebral hemoglobin (CHb) and CHbO2 (rScO2 = CHbO2/CHb + CHbO2) . The rScO2 is the mean oxygen saturation of cerebral arterial, venule, and capillary blood; the venule data is predominate . Infrared light reveals the extent of saturation of the so-called watershed zone (a mixture of 33% arterial and 67% venous blood at a depth of 1-1,5 cm) . The NIRS probe was placed on both sides of the frontal lobe; the probe was cleaned before placement. The first measured value served as the basal value; rScO2 changes were then recorded at 2-s intervals to 60 s and the mean calculated. The cerebral rScO2 is normally 50-80, but may vary by 10-20% at any time . A decrease >20% for patients with a basal cerebral rScO2 value >50 and a decrease >15% for those with a basal cerebral rScO2 <50 indicate cerebral ischemia . Data were captured at 0.1 Hz and collected for 10 min, after application in each position consequently. Cerebral fractional oxygen extraction (cFOE) was calculated for 5th and 10th min average as ( (SpO2-rScO2)/SpO2 ) (SpO2: pulse oximetry oxygen saturation) for each position, which reflects the balance between oxygen delivery and consumption in the tissue .

An infant/pediatric sensor (Covidien INVOS 5100C) costs between \$110 and \$140 each. No outside funding was used for the budget in this study. Within the budget and time period, the maximum number of patients enrolled in the study.

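### Does the lack of a left/right rule and an averaging window for rScO2 and cFOE leave the position comparison undefined?

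*Combined protocol and SAP*

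**What the plan says.** The Materials and Methods section says that infants "were placed supine, on the right or left side, or prone (15/group"), which can be read as three groups or four. Section 2 (Medical records and vital parameters) fixes the side for pulse oximetry: "The probe was placed preductally (on the right wrist) and then connected to the oximetry". It justifies using oximetry "because the relationship between position and saturation and cerebral oximetry was evaluated", so cerebral oximetry by position is a central outcome. It also sets the time frame: "All evaluations commenced 30 s after delivery and terminated at 10 min".

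Section 3 (Cerebral oxygenation) says "The NIRS probe was placed on both sides of the frontal lobe". It reports mean values at the 5th and 10th minutes. Taking the first reading as basal, it says that changes "were then recorded at 2-s intervals to 60 s and the mean calculated". It then adds: "Data were captured at 0.1 Hz and collected for 10 min, after application in each position consequently". It gives the cFOE formula, (SpO2 − rScO2)/SpO2, "for each position, which reflects the balance between oxygen delivery and consumption in the tissue".

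Neither section 3 nor the Statistical Analyses section says which side supplies the analysed rScO2. The repeated-measures model named there has no side factor.

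**The concern.** Body side is part of the allocated position. A sensor on the right forehead lies lower when the infant is on the right side and upper when on the left side. If the two sides read differently, the choice of sensor decides what a right-left comparison measures, and applying the same rule in every arm does not remove this. The side was fixed for SpO2, which makes its absence for rScO2 stand out.

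The timing text raises a second doubt. The 60-s mean is described after the basal reading and is not attached to 5 or 10 min. Two recording rates appear without a stated link. Ten minutes of collection after sensor application does not fit inside a period that runs from 30 s to 10 min. The closing words about each position could suggest that each infant went through several positions. At stake would be whether a reader could reproduce rScO2 and cFOE, and whether a right-left difference reflects position or sensor side.

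**Working it through.** The plan gives no figure on this point. The total of 37 in section 4 (Sample Size) comes without an endpoint, effect size or SD, so it cannot be reproduced and does not help here.

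**Inputs.** From the documents: 15 per group, two-sided 5% level, LSD comparisons after one-way ANOVA, total of 37, measurement from 30 s to 10 min. Assumed, because the documents do not give them: lower-minus-upper difference d of 2 to 6 points, SD of 8 (range 6 to 10), left-right correlation of 0.5 to 0.9, SpO2 of 85 to 95.

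**Side rule, four groups.** Let a lateral infant read m + d/2 on the lower side and m − d/2 on the upper side.
- Right sensor: right minus left = (m + d/2) − (m − d/2) = +d.
- Left sensor: −d. Mean of both: 0.
- With one sensor, each lateral group shifts by d/2 against supine or prone, if those positions have no side difference of their own.

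SE = 8 × √(2/15) = 2.92. From the noncentral t with 4 × 14 = 56 df, the one-sensor right-left test is significant with probability:

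| SD | d | Probability |
|---|---|---|
| 8 | 2 | 0.103 |
| 8 | 4 | 0.270 |
| 8 | 6 | 0.523 |
| 10 | 2 | 0.084 |
| 6 | 6 | 0.768 |

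With the mean of both sides it is 0.05. If LSD is run only after a significant ANOVA, 40,000 simulated trials at SD 8 give about 0.045, 0.14 and 0.33 for d = 2, 4 and 6, against 0.019 with the mean.

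At the stated total of 37 split four ways (9.25 per group, 33 df), SE = 8 × √(2/9.25) = 3.72, and the range for d of 2 to 6 falls to 0.08–0.35.

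**Side rule, three groups.** There is then no right-left arm comparison. At an 8/7 split of one lateral group, a one-sensor mean moves by (1/15) × (d/2) = d/30, which is 0.07 to 0.20 points. The SD becomes √(64 + d²/4) = 8.06 (d = 2) to 8.54 (d = 6), a rise of 0.8% to 6.8%.

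**cFOE.** A shift of d in rScO2 moves cFOE by d/SpO2: from 2/95 = 0.021 to 6/85 = 0.071.

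**Precision.** The SD of the two-side mean relative to one side is √((1 + r)/2): 0.866 at r = 0.5 and 0.975 at r = 0.9. That is equivalent to 15/0.75 = 20.0 or 15/0.95 = 15.8 infants per group.

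**Timing.**
- A 60-s window ending at, centred on or starting at 5 min is centred at 4.5, 5.0 or 5.5 min. Near 10 min the same three windows end at 10.0, 10.5 and 11.0 min, so only the first stays within the stated limit.
- Readings every 2 s give 30 per minute and 0.1 Hz gives 6. The two may be separate phases.
- Collection for 10 min from 30 s ends at 10.5 min, 30 s past the limit.
- Sequential positions would need 3 × 10 = 30 or 4 × 10 = 40 min against 10 − 0.5 = 9.5 min available. That reading therefore conflicts with the clock as well as with the parallel allocation in Materials and Methods.

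**The case for a change.** The strongest case for acting is that side is tied to the randomised factor. The +d, −d or 0 result is algebra, cerebral oximetry is central to the study, and stating the rule costs one sentence. It is also true that the text does not attach the 60-s mean to 5 or 10 min, and that it gives no rule matching the SpO2 in cFOE to the rScO2 average.

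The omission and the algebra stand. The size attached to them does not hold up as harm, for four reasons.
- The 10–52% figures are power to detect an assumed real lower-upper difference, not a false-positive rate. At d = 0 the rules differ only in precision.
- They need four groups. The allocation text can equally be read as one lateral group, where the effect is small.
- They need the head to turn with the trunk, and no section gives head orientation. Section 1 (Infant positioning) even says that all infants were placed supine, which sits awkwardly with lateral measurement.
- Section 3 speaks of a single probe and prices sensors individually under a limited budget, so two retained channels cannot be assumed.

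As for timing, the 60-s mean is the only averaging procedure described and is the natural window. Any window, clock or recording rate applied alike to randomised groups leaves the comparison unbiased.

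**Conclusion.** No change to the plan follows. The plan omits a measurement detail, but no rule that it states produces a wrong result. An analyst with two channels would ordinarily average them, which makes the right-left contrast zero under the model above and improves precision. An analyst with one channel would name the sensor. The 60-s mean would be taken as the window at 5 and 10 min. The overlap of clock and collection time, the two recording rates and the remark about each position are loose wording, best read in line with the parallel allocation.

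The residual risk is confined to one configuration: separate right and left groups, a one-sensor rule, the head following the trunk, and a real lower-upper difference. There, with d of 2 to 6 points and SD 8, the right-left test is significant in 10–52% of trials with 15 per group, or 8–35% at a total of 37. With one lateral group the mean shifts by d/30. All of these sizes rest on an assumed d and SD. Naming the side and window used, and whether right and left formed one group or two, belongs to ordinary reporting of the results.

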#### **4. Sample Size:**

In the investigators' center, monthly birth rate is 300 and since our hospital is the largest perinatology center in our region; the number of births with maternal and neonatal problems is high. When the investigators evaluated our records for the number of infants who were born  $> 37$  GA with CS under spinal anesthesia and did not require any resuscitation efforts; the number was approximately 15 per month. ( $P=0.05$ ) with a 2-sided a error of 5% and power of 80%, a total sample size of 37 total was required.

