### **Statistical Analyses:**

SPSS 25.0 (IBM Corporation, Armonk, New York, United States) and PAST 3 (Hammer, Ø., Harper, D.A.T., Ryan, P.D. 2001. Paleontological statistics) programs were used in the analysis of the variables. The conformity of univariate data to normal distribution was evaluated with the Shapiro-Wilk francia test, while homogeneity of variance was evaluated with the Levene test. Mardia for the conformity of multivariate data to normal distribution; while the (Dornik and Hansen omnibus) test was used, the Box-M test was used for variance homogeneity. In the comparison of more than two groups according to quantitative data, Fisher's Least Significant Difference (LSD) tests were used for One-Way Anova post hoc analysis, one of the parametric methods, Kruskal-Wallis H Test, which is one of the nonparametric tests, was used with the results of Monte Carlo simulation technique, and Dunn's Test was used for Post Hoc analyses. The Paired-Samples T test was tested using Bootstrap results, while the Wilcoxon Signed Ranks Test was tested using the monte carlo simulation method to compare two replicate measurements of dependent quantitative variables with each other. While Friedman's Two-Way test was tested using the monte carlo simulation method to test the variables with more than two repeated measurements and to examine the interaction according to the groups, the General Linear Model-Repeated Anova test from parametric methods was used, and the LSD test was used for Post Hoc analyses. In the comparison of categorical variables with each other, Fisher-Freeman-Holton test was tested with Monte Carlo Simulation technique. While quantitative variables were expressed as mean (standard deviation) and Median (Percentile 25 / Percentile 75) in the tables, categorical variables were shown as n (%). The variables were analyzed at 95% confidence level, and a p value less than 0.05 was considered significant.

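### A basal rScO2 is collected for each infant, but no stated comparison of positions uses it; the cost is precision, and the timing of that reading must be fixed before it can be a covariate

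*Combined protocol and SAP*

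**What the plan says.** Section 3 defines a starting value per infant ("The first measured value served as the basal value; rScO 2 changes were then recorded at 2-s intervals to 60 s and the mean calculated") and gives the rScO2 outcomes as two later values: "the mean values at 5 th and 10 th min were recorded using a Covidien INVOS 5100C instrument". The basal value reappears only in a literature threshold for cerebral ischemia ("A decrease >20% for patients with a basal cerebral"), which is not set up as an endpoint to compare between positions.

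For group comparisons, the Statistical Analyses section says: "In the comparison of more than two groups according to quantitative data, Fisher's Least Significant Difference (LSD) tests were used for One-Way Anova post hoc". It adds Kruskal-Wallis with Dunn's test as the nonparametric route, and a General Linear Model repeated ANOVA for variables measured more than twice, with a look at the interaction with group. It names no covariate, no analysis of covariance and no change-from-basal outcome, and it does not say which variable goes into which test.

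On timing, section 2 says: "All evaluations commenced 30 s after delivery and terminated at 10 min". Section 1 describes first care under the radiant heater. Section 3 describes NIRS data collection as following application in each position. None of these places the first NIRS reading before or after the infant is turned.

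**The concern.** Cerebral oxygenation is one of the things the study sets out to relate to position. Groups are small (infants "were placed supine, on the right or left side, or prone (15/group"), and section 3 says that budget and time capped enrolment. When infants cannot be added, a starting value already in the data is the cheapest source of precision.

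If infants who start high tend to stay high, part of the spread in rScO2 at 5 and 10 min is already present at the basal reading. Without a covariate, that part stays in the error term. Power is then lower than it need be, and confidence intervals for differences between positions are wider.

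**Working it through.** **The plan's own figure.** Section 4 says: "with a 2-sided a error of 5% and power of 80%, a total sample size of 37 total was required". It gives no outcome, effect size, SD or test, so 37 cannot be reproduced. Solved backwards with a one-way ANOVA, 37 infants give 80% power at Cohen's f of about 0.53 with three groups or 0.58 with four. This does not supply an effect size for rScO2, so one is assumed below.

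**Inputs.**
- From the documents: 15 infants per group; two-sided alpha 5%. The text can be read as three groups (45 infants) or four (60), depending on whether right and left side are one group or two.
- Assumed: one position shifted by 0.8 SD; r = 0.3, 0.5 or 0.7; the same SD at basal and follow-up; a linear relation.

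**Step 1: residual variance.** Adjustment multiplies the error variance by 1 − r²:
- r = 0.3: 1 − 0.09 = 0.91, a 9% cut
- r = 0.5: 1 − 0.25 = 0.75, a 25% cut
- r = 0.7: 1 − 0.49 = 0.51, a 49% cut

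**Step 2: power of the overall F test.** With k groups of 15 and one mean shifted by 0.8 SD, the noncentrality is λ = 15k × 0.8² × (k − 1)/k².
- k = 4: 60 × 0.64 × 3/16 = 7.2
- k = 3: 45 × 0.64 × 2/9 = 6.4

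Adjustment divides λ by 1 − r² and takes one error degree of freedom (56 to 55 for k = 4; 42 to 41 for k = 3).

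| r | λ, k = 4 | Power, k = 4 | λ, k = 3 | Power, k = 3 |
|---|---|---|---|---|
| unadjusted | 7.20 | 57% | 6.40 | 58% |
| 0.3 | 7.91 | 61% | 7.03 | 62% |
| 0.5 | 9.60 | 71% | 8.53 | 71% |
| 0.7 | 14.12 | 87% | 12.55 | 87% |

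**Step 3: chance imbalance.** The difference in basal means between two groups of 15 has standard error √(2/15) = 0.37 SD, a 95% chance range of ±1.96 × 0.365 = ±0.72 SD. It exceeds 0.5 SD in about 17% of pairwise contrasts.

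Only r times the imbalance is expected to carry into the follow-up difference. For a 0.5 SD imbalance that is 0.15 SD at r = 0.3, 0.25 SD at r = 0.5 and 0.35 SD at r = 0.7.

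**Step 4: what this does to the error rate.** Over all randomizations the unadjusted test stays at 5%, because its error term already contains the variation between infants. Given that a 0.5 SD imbalance has occurred, the false-positive rate of a 5% pairwise test (normal approximation) is about 6%, 7% and 8% at r = 0.3, 0.5 and 0.7.

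**Step 5: change from basal as an alternative.** A change score has variance 2(1 − r) times the raw variance: 1.4 at r = 0.3, 1.0 at r = 0.5 and 0.6 at r = 0.7. It helps only when r exceeds 0.5, whereas covariate adjustment reduces residual variance at any nonzero r.

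**The case against.** **The basal value may already be used.** The plan assigns no variable to any test. If basal, 5-min and 10-min rScO2 were entered as three levels of the repeated ANOVA, the time-by-position interaction would use the basal value. Section 3 also speaks of rScO2 changes after the basal value. This stands in part: a reader might infer that the basal value is ignored in every analysis, but the documents support only that no use is stated. Against the objection, the rScO2 means are listed at two times only, while heart rate, pulse oximetry and perfusion index, each recorded at three times, fit that model more naturally.

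**Randomization takes care of starting differences.** This stands. A reader might infer that chance imbalance passes in full into the 5- and 10-min differences, or that the planned comparison is biased. Steps 3 and 4 show neither is so.

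**The correlation may be low.** This also stands. The normal range of 50 to 80 in section 3 may suggest a wide, stable spread between infants. The same sentence allows variation of 10–20% at any time, and the source cited for it is titled as a study of cardiac and vascular surgery patients. A single reading soon after birth may predict later values poorly. At r = 0.3 the gain is about 4 points of power. Estimating the slope costs slightly more than the one degree of freedom in step 2: with the usual factor 1 + 1/(N − k − 2), the sample-size equivalents for k = 4 are about 1.08, 1.31 and 1.92, against 1.10, 1.33 and 1.96 from 1/(1 − r²).

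**Adjustment could do harm.** This is the strongest objection. If the first reading is taken after the infant is turned, position may already have affected it, and adjustment could remove part of the effect under study. The documents do not rule this out, so covariance analysis cannot be recommended unconditionally.

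**Conclusion.** The point holds as one about precision. A basal rScO2 is collected and no comparison of positions is stated to use it. The validity of the unadjusted test is not in question.

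The possible gain runs from about 4 points of power at r = 0.3 to about 30 at r = 0.7 (57% to 61% and 87%, four groups; three groups are similar). Both r and the 0.8 SD shift are assumptions, and the lower end is plausible for a single early reading. The gain is safely available in the main analysis only if the basal reading precedes placement in the allocated position, which the documents leave open. The calculation covers rScO2 only; cFOE, which is derived from it, would need its own decision.

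**What to change.** 1. State in section 3 whether the basal rScO2 is read before or after the infant is placed in the allocated position, and reconcile this with section 1 and with the sentence on data collection in each position.
2. If before: compare 5- and 10-min rScO2 by analysis of covariance, with position as factor and basal rScO2 as covariate. Where the nonparametric route applies, do this on ranks. Report adjusted differences between positions with 95% confidence intervals.
3. If after: keep the unadjusted comparison as the main analysis and give the adjusted one only as a sensitivity analysis.
4. Say which test is applied to rScO2, so that it is clear whether the basal value enters the repeated ANOVA.

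The cost is one degree of freedom, a sentence on timing and a line of analysis wording. No further infants or measurements are needed for either branch.

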#### **4. Sample Size:**

In the investigators' center, monthly birth rate is 300 and since our hospital is the largest perinatology center in our region; the number of births with maternal and neonatal problems is high. When the investigators evaluated our records for the number of infants who were born  $> 37$  GA with CS under spinal anesthesia and did not require any resuscitation efforts; the number was approximately 15 per month. ( $P=0.05$ ) with a 2-sided a error of 5% and power of 80%, a total sample size of 37 total was required.

### **Statistical Analyses:**

SPSS 25.0 (IBM Corporation, Armonk, New York, United States) and PAST 3 (Hammer, Ø., Harper, D.A.T., Ryan, P.D. 2001. Paleontological statistics) programs were used in the analysis of the variables. The conformity of univariate data to normal distribution was evaluated with the Shapiro-Wilk francia test, while homogeneity of variance was evaluated with the Levene test. Mardia for the conformity of multivariate data to normal distribution; while the (Dornik and Hansen omnibus) test was used, the Box-M test was used for variance homogeneity. In the comparison of more than two groups according to quantitative data, Fisher's Least Significant Difference (LSD) tests were used for One-Way Anova post hoc analysis, one of the parametric methods, Kruskal-Wallis H Test, which is one of the nonparametric tests, was used with the results of Monte Carlo simulation technique, and Dunn's Test was used for Post Hoc analyses. The Paired-Samples T test was tested using Bootstrap results, while the Wilcoxon Signed Ranks Test was tested using the monte carlo simulation method to compare two replicate measurements of dependent quantitative variables with each other. While Friedman's Two-Way test was tested using the monte carlo simulation method to test the variables with more than two repeated measurements and to examine the interaction according to the groups, the General Linear Model-Repeated Anova test from parametric methods was used, and the LSD test was used for Post Hoc analyses. In the comparison of categorical variables with each other, Fisher-Freeman-Holton test was tested with Monte Carlo Simulation technique. While quantitative variables were expressed as mean (standard deviation) and Median (Percentile 25 / Percentile 75) in the tables, categorical variables were shown as n (%). The variables were analyzed at 95% confidence level, and a p value less than 0.05 was considered significant.

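### With four positions, Fisher's LSD does not hold at 5% the chance of at least one false pairwise difference when one position truly differs: about 12% from a 1 SD shift upward, less below that.

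*Combined protocol and SAP*

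**What the plan says.** Materials and Methods randomizes babies by envelope; they were "placed supine, on the right or left side, or prone (15/group". The Statistical Analyses section compares more than two groups by one-way ANOVA when the parametric conditions are met and adds that "Fisher's Least Significant Difference (LSD) tests were used for One-Way Anova post hoc analysis". For variables measured more than twice it uses a repeated-measures general linear model, after which "the LSD test was used for Post Hoc analyses". The threshold is that "a p value less than 0.05 was considered significant".

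The section describes no multiplicity adjustment for the pairwise comparisons. It also does not say whether LSD is read only after a significant overall F test.

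**The concern.** Four positions give 4 × 3 / 2 = 6 pairs. A significant F protects LSD at 5% when all groups are equal, and it does so in every configuration only when there are three groups. With four groups, a real effect of one position can carry the F test past its threshold. The three pairs among the remaining positions are then each tested at an unadjusted 5%.

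A positioning study is read through its pairwise results: which position differs from which. The weakness appears when there is a real effect, which is when readers turn to those results. Naming a single primary outcome at a single time would not remove it, and it does not depend on unequal variances.

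**Working it through.** **The plan's own figure.** The plan states no error rate for the family of pairs, so there is none to reproduce. The only planning figure is in the Sample Size section: "with a 2-sided a error of 5% and power of 80%, a total sample size of 37 total was required". It cannot be reproduced because no outcome, effect size or SD is given. Solving backwards, a total of 37 in four groups would need Cohen's f of about 0.58. The results below do not use it.

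**Inputs.**
- From Materials and Methods: k = 4 groups, n = 15 per group, so error df = 4 × (15 − 1) = 56.
- From Statistical Analyses: p<0.05 per test.
- Assumed: normal data, equal SDs, one position shifted by a multiple of the SD and the other three equal.

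**Step 1, limiting rate.** The LSD critical value is t(0.975; 56) = 2.003. At least one of the three null pairs is declared different when the studentized range of three means exceeds √2 × 2.003 = 2.833. With 56 df that probability is 12.1%. Treating the three tests as independent would give 1 − 0.95³ = 14.3%; this is only an upper bound, because the pairs share means.

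**Step 2, LSD read only after F at p<0.05.** Simulation, 200,000 trials per setting:

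| Shift of one position | F test significant | At least one false pair among the three equal positions |
|---|---|---|
| 0 (all equal) | 5.0% | 5.0% |
| 0.25 SD | 9.1% | 5.0% |
| 0.5 SD | 24.3% | 7.7% |
| 0.75 SD | 51.0% | 10.4% |
| 1.0 SD | 78.2% | 11.6% |
| 1.25 SD | 94.0% | 12.0% |
| 1.5 SD | 99.0% | 12.0% |
| 3 SD | 100% | 12.0% |

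In the first row all four positions are equal, so all six pairs count. If two positions differ equally from the other two, the rate is about 9.6%.

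**Step 3, LSD read without the F gate.** The rate is about 12% at any non-zero shift. When all four positions are equal it is the probability that the range of four means exceeds 2.833, which is 19.9%.

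**Step 4, one named pair.** For a single null pair, such as right versus left side, gated LSD stays at or below about 5% at every shift.

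**Step 5, three groups.** If right and left side form one group, gated LSD gives 4.9% to 5.1%.

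**Step 6, alternatives with four groups of 15.**
- Fisher-Hayter uses the studentized range for k − 1 = 3 means: 3.405 / √2 = 2.41. The false-pair rate is at most about 5%.
- Tukey uses the range for 4 means: 3.745 / √2 = 2.65. The rate is 2.8%.
- Power for one truly different pair at 1 SD: LSD about 69%, Fisher-Hayter about 61%, Tukey 54%. At 1.25 SD: about 89%, 83% and 78%.

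**The case against.** **The number of groups.** Read by its commas, the list of positions could have three items, with the two sides as one, and with three groups the problem disappears. Other text adds doubt. The Infant positioning section says that all babies were placed supine, the Cerebral oxygenation section can be read as positions applied in turn, and the stated total of 37 is not 4 × 15 = 60. Four groups remains the natural reading of the randomization sentence, but the point depends on it. The total of 37 does not rescue LSD: with 9 per group the limiting rate is still 12.0%.

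**The size.** A reader might infer that the risk is 12% whenever one position differs. It is not. At 0.25 SD there is no inflation, and at 0.5 SD the F test is passed only about a quarter of the time. Since the documents give no SD or effect size, a shift of 1 SD or more is an assumption. It is, however, about where F has 80% power with 15 per group.

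**The standard.** A reader might also infer that the plan promises 5% across the six pairs and breaks that promise. It states a per-test threshold only, and each single null pair respects it. Asking for control over the set of pairs is a judgement, though a reasonable one when the conclusion is a ranking of positions.

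**Repeated measures.** It is tempting to extend the 12% to the LSD used after the repeated-measures model. The text does not say whether that LSD compares positions or times. The Medical records section lists three times (2, 5 and 10 min), and gated LSD on a three-level factor does not have this defect. No repeated-measures model was simulated.

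**The rank route.** A reader might infer the same weakness there, since "Dunn's Test was used for Post Hoc analyses" with no adjustment stated. The documents do not say that it is unadjusted. Even unadjusted, the simulated rate after Kruskal-Wallis falls as the shift grows: 8.8% at 1 SD, 7.5% at 1.5 SD and 2.8% at 3 SD. It is not part of this point.

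**Conclusion.** The point holds for pairwise comparisons of four positions after one-way ANOVA. Gated LSD keeps 5% when all positions are equal, but not in general when one differs. The chance of at least one false pair among the other three rises from about 5% at 0.25 SD to a ceiling of about 12% from 1 SD. If the gate, which the plan does not mention, is not applied, the chance is about 20% when all four are equal.

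This rests on four independent groups of 15, normal data and equal SDs. The documents do not support saying that a particular null pair has a 12% risk, or that every LSD comparison in the plan is affected. The weakness is well defined, moderate and inexpensive to remove: a cheap improvement, not a flaw that invalidates the analysis.

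**What to change.** In Statistical Analyses, for pairwise comparisons between positions on the parametric route, replace LSD by one of the following:

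- **Fisher-Hayter.** Test pairs only if the ANOVA F has p<0.05, then require |t| > 2.41 with four groups of 15, instead of 2.00. With other group sizes the critical value must be recomputed. With three groups this is identical to gated LSD, so the wording is safe on either reading of the randomization sentence.
- **Tukey's HSD.** A one-step procedure, more conservative here.

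Apply the same rule to LSD after the repeated-measures model only where it compares positions, and say which comparisons those are. State in Materials and Methods whether right and left side are separate groups.

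The cost is a wording change and a recalculation of the pairwise results, with no extra babies or data. The downside is power: for a 1 SD difference it falls from about 69% to about 61% (Fisher-Hayter) or 54% (Tukey). With about 9 per group, near the stated total of 37, it falls from about 42% to about 35% with Fisher-Hayter. The documents do not show whether the named software offers Fisher-Hayter directly, but the pairwise t statistics can be compared with the critical value by hand.
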